11.0 STATISTICAL ANALYSES

Sample Size

There was only one study^[14] that provided appropriate data for a power analysis for the primary outcome, pain, and one study that provided appropriate data for the primary outcome, anxiety^[39]. The sample size requirements based on the results from each of the studies are displayed in the following tables. Since our time points differ from these two studies, we have chosen to perform an interim analysis after approximately 55-60% (14-15 per group depending on enrollment pace) of patients have been enrolled in order to re-estimate the required sample size. Our current sample size enrollment (50 patients) is simply based on what the study team considers the maximum number of patients that can be feasibly enrolled within the anticipated study enrollment time-frame. As shown, this number of patients (50) are more than double that of the estimated sample size needed (22) at 90% power, while accounting for 10% attrition.

Primary Outcomes: Pain

Study: Chen et al. 2015

	Measurement Method: VAS (made relative to 0-10 scale)	Total N [contact] power	Total N needed accounting for 10% attrition	Total N [contact] power	Total N needed accounting for 10% attrition
--	---	-----------------------------	---	-----------------------------	---

Post-Op Time	Group difference (mean±SD)				
2 hr	1.4±0.9	16	18	20	22
4 hr	1.2±0.4	8	10	8	10
8 hr	0.8±0.1	4	6	4	6
12 hr	1.0±0.2	6	8	6	8
24 hr	0.8±0.1	4	6	4	6

Primary Outcomes: Anxiety

Study: Karst et al. 2006 (treatment vs no treatment)

Measurement Method (time change)	Group Mean difference of change score	N [contact] power	N needed accounting for 10% attrition	N [contact] power	N needed accounting for 10% attrition
STAI (Baseline post-treatment)	2.83±0.72	6	8	6	8
VAS (Baseline to post-treatment)	1.44±0.34	6	8	6	8

An interim analysis was performed using data for the primary outcomes, *pain* and *anxiety*. Of note, this interim analysis was performed to re-estimate the sample size since the initial sample size estimate was based on a study with different time points than this study. Therefore, the sole purpose of this interim analysis was to re-estimate the sample size, and was not to test the hypothesis.

For the primary aim *pain*, based on data from the first 31 patients enrolled, our sample size calculation indicates that a minimum of 26 subjects per group are needed using a repeated measures design (each subject is measured 4 times) with 2 groups for a total of 52 subjects. This design achieves 81% power to test factor B1 if a Geisser-Greenhouse Corrected F Test is used with a 5% significance level and the actual effect standard deviation is 0.255 (an effect size of 0.40319). We estimate an attrition rate of 10%, which will require 58 subjects; however we will aim to enroll 60 subjects (30 per group). For the second primary aim *anxiety*, we performed two sample size calculations. One based on the data of all 17 patients in the acupuncture group, and another excluding the 3 patients for which protocol deviations were reported due to methods collecting the anxiety measure. With all 17 patients, the difference in the response of anxiety from pre to post acupuncture was normally distributed with a standard deviation 26.27. If the true difference in the mean response of matched pairs is 35.64, we will need to study 6 pairs of subjects to be able to reject the null hypothesis that this response difference is zero with probability (power) 0.8. The Type I error probability associated with this test of this null hypothesis is 0.05. With the 3 patients removed, the difference in the response of anxiety from pre to post acupuncture was normally distributed with standard deviation 26.588. If the true difference in the mean response of matched pairs is 39.14, we will need to study 6 pairs of subjects to be able to reject the null hypothesis that this response difference is zero with probability (power) 0.8. The Type I error probability associated with this test of this null hypothesis is 0.05.

Pain is the more appropriate primary outcome of the two primary outcomes to base the sample size on because there are 4 time points of data for each group for this variable. The other primary outcome, *anxiety* does not have a post measure for the control group (per the study design), and therefore a within-group pre to post change in the acupuncture group is being performed to examine this outcome. We acknowledge that this within group design is weaker than the design to assess the pain outcome measure.

Statistical Methods

Patient demographic and clinical (including operative) characteristics will be compared between groups using an independent samples t-test if continuous data are normally distributed), or Mann Whitney U if continuous data are not normally distributed. A chi-square or Fisher's exact test (if cell counts are <5) will be used to compare these characteristics between groups for categorical variables. All continuous variables will be expressed as mean±SD or median, IQR as appropriate. Categorical variables will be expressed as frequency (%).

The primary and secondary study outcomes will be compared between groups two ways. First, an independent samples t-test or Mann Whitney U test if deemed more appropriate for the scale data (which may be considered ordinal) will be used to compare outcomes at each time point between the two groups. Second, a mixed model for repeated measures will be used to compare the study outcomes that are repeated over time (e.g., Pain). This model was chosen instead of a repeated measures ANOVA due to the ordinal nature of the repeated outcome measures in addition to this test being more appropriate for non-normal residuals, missing data, as well as the ability to treat the time points as discrete categories or as true numbers, which accounts for any variability in when the measures are administered to patients.

We anticipate that the timing of the measures being administered may fluctuate slightly due to measures being taken PostOP.

All analyses will be conducted using SPSS version 26.0. P (2-sided) < .05 will be deemed the level of statistical significance.

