Intra- and postoperative opioid consumption is another commonly studied outcome of acupuncture.^[13] In a randomized controlled trial (RCT) of 54 patients receiving THA, researchers randomized patients to receive either auricular (of the ear) or sham acupuncture treatment and compared the amount of piritramide (a synthetic opioid closely related to fentanyl and commonly used in European countries) used

intraoperatively.^[9] The results showed that patients in the acupuncture group required significantly less piritramide intraoperatively compared with sham (37 ± 18 mg vs. 54 ± 21 mg). A similarly constructed RCT also studied the effects of preoperative auricular acupuncture on intraoperative opioid use, but researchers instead studied fentanyl use and included patients undergoing TKA.^[14] These researchers, too, found that patients in the acupuncture group required significantly less opioid during surgery than patients in the sham acupuncture group (620.7 ± 258.2 μ g vs. 868.6 ± 319.3 μ g). Further, these patients on average lasted longer before requesting analgesia and exhibited lower visual pain scores. Several other studies have also demonstrated that preoperative acupuncture lessens the need for opioids during and after surgery.^[4,10,15,16] Reducing opioid consumption through the introduction of safely administered acupuncture poses a potential net improvement for patient safety and hospital costs.

Perhaps the most commonly cited benefit of acupuncture is increased relaxation and decreased anxiety, and several systematic reviews have reported that these benefits persist in the clinic.^[1,3,17] For patients with anxiety, depression, or other mental ailments, this is an important finding considering the substantial evidence linking poor mental health with significantly worse surgical outcomes.^[18-27] For example, one systematic review that accounted for 53,562 patients undergoing THA concluded that depression and anxiety were associated with increased postoperative pain, and another that accounted for 95,560 patients undergoing TKA found that the most consistent and significant indicator of dissatisfaction related to surgery was preoperative anxiety.^[27,28] Despite this evidence that poor preoperative mental health is detrimental to both practitioners and patients of surgery, there are currently no guidelines for improving preoperative mental health conditions.^[25]

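### Section 11 still presents 50 patients as more than double the 22 needed at 90% power, although its own re-estimate asks for 52 evaluable (58 with attrition, target 60) at 81% power

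*Combined protocol and SAP*

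**What the plan says.** The Sample Size part of section 11.0 opens with two tables of required N taken from the literature, one for pain and one for anxiety. It describes 50 as the current enrolment figure, "simply based on what the study team considers the maximum number of patients that can be feasibly enrolled", and adds that "this number of patients (50) are more than double that of the estimated sample size needed (22) at 90% power", allowing for 10% attrition. The 22 is the 2 hr pain row (difference 1.4, ± 0.9), in a column headed "Group difference (mean±SD"). The same paragraph explains that the cited studies used different time points, so the size would be re-estimated at an interim look.

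The re-estimate follows in the same section. From the first 31 patients, "our sample size calculation indicates that a minimum of 26 subjects per group are needed using a repeated measures design", which is 52 in total. "This design achieves 81% power to test factor B1 if a Geisser-Greenhouse Corrected F Test is used with a 5% significance level", with an effect standard deviation of 0.255 and an effect size of 0.40319. With 10% attrition the requirement becomes 58, and the team aims for 60 (30 per group).

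Section 3.1 still gives the target as 50, 25 per group.

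**The concern.** A trial of 50 cannot be more than twice as large as needed for 90% power and also smaller than the minimum for 81% power on the same outcome. Both statements stand in current text, and neither says that it replaces the other. The 50-versus-22 comparison is written in the present tense, and section 3.1 carries the old target as the operative one.

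Two things are at stake. Someone who relies on the comparison would believe the pain analysis has a wide margin and could read a null result as stronger evidence of no effect than it is. Someone who relies on section 3.1 could regard recruitment as complete at 50, below all three re-estimated figures.

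The tables behind the initial estimate also invite a question. Apart from the 2 hr row, they imply standardised effects of about 3 to 8, which is very large for a patient-reported scale.

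**Working it through.** **Inputs, all from section 11.0.** Two-sided test: "P (2-sided) < .05 will be deemed the level of statistical significance". Pain rows of the literature table: 1.4±0.9, 1.2±0.4, 0.8±0.1, 1.0±0.2, 0.8±0.1. Anxiety rows: 2.83±0.72 and 1.44±0.34. Re-estimate: effect SD 0.255, f = 0.40319, two groups, four measures per patient, 10% attrition. The power levels in the table headers are masked. I took them as 80% and 90%; the text confirms the 90%, and reproduction supports both.

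**Step 1: reproduce the 22.** Use an exact two-sample t-test with equal groups and d = difference / ± value.
- 2 hr: d = 1.4/0.9 = 1.56, total N = 16 (80%) and 20 (90%).
- 4 hr: d = 3, N = 8 and 8.
- 8 hr and 24 hr: d = 8, N = 4 and 4.
- 12 hr: d = 5, N = 6 and 6.
- Anxiety: d = 3.93 and 4.24, N = 6 and 6.

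Every pre-attrition N matches, so the ± values were used as patient-level SDs. The attrition step is 20 × 1.1 = 22; dividing instead gives 20/0.9 = 22.2, which rounds up to 23. Only the 2 hr row leads to 22.

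**Step 2: reproduce the 81%.** Take B1 as the between-group factor. Power = P(F′ > F_crit), where F′ is noncentral F with 1 and N − 2 degrees of freedom and λ = N × f². At N = 52, λ = 52 × 0.40319² = 8.45 and power is 81.4%, against the stated 81%. Attrition: 52/0.9 = 57.8, rounded up to 58, as stated.

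**Step 3: apply the same method to the other sizes.**

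| Enrolled | Evaluable after 10% attrition | Power | Power with no attrition |
|---|---|---|---|
| 22 | 20 | 40.0% | 43.7% |
| 50 | 45 | 75.3% | 79.8% |
| 60 | 54 | 82.8% | 86.7% |

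With equal groups, 66 evaluable gives 89.7% and 68 gives 90.6%. So 90% needs 68 evaluable, and 68/0.9 = 75.6, about 76 enrolled.

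**Step 4: why the two estimates differ.** The re-estimate implies an SD of 0.255/0.40319 = 0.63 for a patient's mean over four measures. Assuming equal variances and a common correlation ρ, the single-time SD is 0.63/√((1 + 3ρ)/4). That is 0.63 at ρ = 1, 0.80 at ρ = 0.5 and 1.26 at ρ = 0. The documents do not give ρ. The 2 hr value of 0.9 lies inside this range; the values 0.4, 0.1, 0.2 and 0.1 lie below it.

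For two equal groups the implied mean difference is 2 × 0.255 = 0.51 points, against 1.4 in the 2 hr row. The smaller difference is therefore the main source of the gap. The 0.51 is an average over four measures and the 1.4 belongs to one time point, so the comparison is indicative only.

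**The case against.** The section largely explains itself. It warns that the time points differ, says that 50 rests on feasibility, refers to the tables as the initial estimate, and goes on to the re-estimate and the target of 60. A careful reader arrives at the right figure, so over-reading of a null result is a risk and not a certainty. That is fair, and it makes this a matter of leftover text. It does not remove the conflict: the comparison with 22 is still asserted as current, and section 3.1 is unchanged.

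The power figures rest on an imprecise effect size. Assume that f is the observed interim effect and that the 31 patients split 17 and 14 (17 is the stated acupuncture count). Then d = 2f = 0.81 with SE √(1/17 + 1/14 + 0.81²/62) = 0.375, and an approximate 95% interval of 0.07 to 1.54. Power with 20 evaluable then runs from about 5% to 90%. This stands: the percentages are conditional on the plan's own estimate and should be labelled so.

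A reader might go further and infer that the ± values behind the 22 cannot be patient-level SDs. The documents do not support that. The 0.9 is labelled an SD and fits the range in Step 4. The ±0.1 and ±0.2 values do look too small, but they do not produce the 22. Showing that they are standard errors would need the source studies.

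Other standardised effects in the documents do not settle it either. The opioid result in section 2.0 (247.9/√((258.2² + 319.3²)/2) = 0.85) concerns a different endpoint. The trial's own anxiety change (35.64/26.27 = 1.36) is within one group, whereas the anxiety table compares treatment with no treatment.

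A reader might also take 40% as the power at 50 patients. It belongs to 22 enrolled.

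**Conclusion.** The point holds as an inconsistency in current text. The claim of more than twofold sufficiency at 90% power conflicts with the plan's own re-estimate, under which neither 50 nor 60 enrolled reaches 90%, and section 3.1 still carries a target below the re-estimated minimum. On the re-estimated effect, stopping at 50 instead of 60 would lower power by about 7 to 8 percentage points.

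This rests on reading B1 as the between-group factor (which reproduces the stated 81%), on 10% attrition, and on f = 0.40319 being the true effect. The ± values outside the 2 hr row warrant a check; that they are wrong is not shown. The planned 60 meets the plan's re-estimated requirement of 58, so the size of the trial is not at issue here.

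**What to change.** 1. In section 11.0, delete the 50-versus-22 sentence or mark it as superseded by 52 evaluable, 58 with attrition, target 60.
2. In section 3.1, replace the target of 50 (25 per group) with 60 (30 per group).
3. State power from the re-estimate only: about 83% with 54 evaluable of 60 enrolled, 90% not reached, conditional on an effect size estimated from 31 patients.
4. Keep the literature tables only as the superseded initial estimate. Check against the sources whether the ± values in the 4 to 24 hr pain rows and the anxiety rows are patient-level SDs, and correct or annotate those rows if they are not.

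The cost is wording in two sections and one look-up in each of the two cited studies. The stated power becomes less favourable. No extra patients and no change of design are requested.

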3.0 OVERVIEW OF STUDY DESIGN/INTERVENTION

3.1 Design

This is a prospective, open-label, randomized controlled trial to determine the efficacy and safety of preoperative acupuncture on high-anxiety patients undergoing TKA or THA. Patients scheduled for THA or TKA to be performed by one of the IRB approved orthopedic surgeons at the BJI will be screened for high preoperative anxiety one week prior to procedure in the PREPARE Center, the BJI's preoperative services clinic, using printed copies of the APAIS questionnaire. The APAIS will be used as a screening tool and is considered optional for the patient to complete and not a standard of care measure. High-anxiety patients consenting to the study will be randomized to receive either 1) preoperative acupuncture (Acupuncture) or 2) no intervention (Control). Results from a quality study at the PREPARE clinic demonstrates that number of patients with high-anxiety entering the clinic is 30 per month. Accounting for the availability of investigators and surgeons, the study period is estimated to last approximately two years to obtain the 50 patients, 25 per group that we aim to enroll in this study. There will be an interim analysis after enrolling 14-15 patients in each group (60%) to re-estimate the sample size using more appropriate data (see sample size estimate section). Each patient will be enrolled in the study from the time of consent and will be followed up to 30 days postoperatively. Investigators performing the acupuncture will be licensed and certified throughout the study duration.

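### Section 3.1 still aims for 50 patients although section 11 re-estimates to 60, and the powered pain effect appears to average in a reading taken before acupuncture

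*Combined protocol and SAP*

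**What the plan says.** Section 3.1 plans for "approximately two years to obtain the 50 patients, 25 per group that we aim to enroll in this study". It then announces an interim re-estimation at 14-15 patients per group and refers the reader to the sample size section.

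Section 11, Sample Size, describes 50 as the current enrolment and as "what the study team considers the maximum number of patients that can be feasibly enrolled within the anticipated study enrollment time-frame". It then reports the interim as already done, adding that "the sole purpose of this interim analysis was to re-estimate the sample size, and was not to test the hypothesis". The pain result is introduced with "based on data from the first 31 patients enrolled, our sample size calculation indicates" a minimum of 26 per group. The calculation assumes four measurements per subject, a 5% level and 81% power for an undefined factor B1, and that "the actual effect standard deviation is 0.255 (an effect size of 0.40319"). Ten percent attrition gives 58; "however we will aim to enroll 60 subjects (30 per group").

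Section 11 prefers pain to anxiety for sizing because "there are 4 time points of data for each group for this variable". The first of its two anxiety calculations is described as "One based on the data of all 17 patients in the acupuncture group".

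Statistical Methods compares outcomes at each time point and also by a mixed model, with a two-sided 0.05 level and no adjustment for the re-estimation. It names neither a single primary pain test nor a role for the pre-operative pain score.

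**The concern.** There are three linked problems.

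- **Two targets.** Current text gives 50 and 60, and 60 exceeds the only ceiling stated without comment. Power at the plan's own effect size depends on which is followed.
- **The powered effect.** Section 1.0 states the aim as postoperative pain. If the four readings behind the 81% include the pre-operative one, the group effect averages in a score that acupuncture cannot have changed. That dilutes any true effect and wastes a useful covariate.
- **Undisclosed inputs.** The plan does not say whether 0.255 reflects the observed interim difference between arms, or whether the SD and correlation were observed or assumed. Not testing a hypothesis at the interim does not by itself secure 5% if the observed difference helped choose N.

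**Working it through.** **1. Reproduce the 81%.** Take a two-group main effect with noncentral F on 1 and N-2 df and noncentrality N × f². With N = 52 and f = 0.40319 this is 52 × 0.40319² = 8.453, and power is 0.814, matching the stated figure. A time or group-by-time test on 3 and 150 df gives 0.668 (noncentrality N × f²) or 0.999 (4 × N × f²), and neither matches. Attrition: 52/0.9 = 57.8, so 58, as stated.

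**2. The two targets.**

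| Enrolled | Analysed (×0.9) | N × f² | Power |
|---|---|---|---|
| 50 | 45 | 7.315 | 0.753 |
| 60 | 54 | 8.778 | 0.828 |

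**3. What f implies.** With two equal groups the effect SD is half the difference, so the difference is 2 × 0.255 = 0.51 points. The standardiser is 0.255/0.40319 = 0.632, a variance of 0.4. For the mean of four equally correlated readings the variance is SD² × (1 + 3ρ)/4. SD 1 with ρ 0.2 gives 1.6/4 = 0.4; SD 0.8 with ρ 0.5 gives 0.64 × 2.5/4 = 0.4. Round assumed values therefore fit exactly, but the documents do not say whether they were used.

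**4. Which four readings.** Sections 7.1 and 7.2 and Table 1 give the control arm one pre-operative pain reading and three in PACU (arrival, 1 h, 3 h). The acupuncture arm has these plus one after acupuncture and before surgery. The four shared readings are thus one before acupuncture and three after surgery.

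**5. Cost of averaging in the first reading (illustration).** Assume a 0.51-point difference at the PACU readings only, SD 1, ρ 0.2 and 54 analysed.

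- Four-reading average: difference 0.51 × 3/4 = 0.3825; d = 0.3825/√0.4 = 0.605; noncentrality 54 × 0.605²/4 = 4.94; power about 59%.
- Three PACU readings, adjusted for the pre-operative score: variance of the mean (1 + 2 × 0.2)/3 = 0.4667; less 0.2² = 0.04 explained by the covariate, 0.4267 remains; d = 0.51/√0.4267 = 0.781; noncentrality 8.23 on 1 and 51 df; power about 80%.

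With SD 0.8 and ρ 0.5 the first figure is unchanged. For the second, the variance is 0.64 × 2/3 - 0.32²/0.64 = 0.2667, d = 0.988, noncentrality 13.17 and power about 95%. If 0.51 is instead already the four-reading average with no difference before acupuncture, the PACU difference would be 0.51 × 4/3 = 0.68. The 81% would then already contain the dilution.

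**6. Type I error if the arm difference set N.** Assume 17 against 14 patients at the interim (17 of the 31 in acupuncture), and an ordinary pooled final test at 1.96.

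- Assumed rule (the plan states none): N for 80% power at the observed difference, allowing 10% attrition and held to 50-60. Two million simulations give 5.2%.
- Worst case, choosing N in 50-60 to maximise the conditional rejection probability at every interim value: 5.5%.

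Conditional error is 1 - Φ[(1.96 - √t × z)/√(1 - t)], with t = 31/N and z = 0.51/(SD × √0.4 × √(1/17 + 1/14)), taking ρ 0.2:

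| Assumed SD | Interim z | N = 50 | N = 60 |
|---|---|---|---|
| 1 | 2.23 | 0.372 | 0.305 |
| 1.5 | 1.49 | 0.101 | 0.100 |
| 2 | 1.12 | 0.040 | 0.048 |

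The direction depends on an SD that the plan does not give.

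**The case against.** Section 3.1 marks its figure as provisional by announcing the re-estimation and pointing to section 11. This is a single-centre trial whose own team set 60, so premature stopping at 50 is not a strong prediction. The 50 was a feasibility judgement, not a statistical bound. This stands as mitigation, but the figure in section 3.1 was not updated and section 11 does not reconcile 60 with its stated maximum.

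The timing and purpose of the interim were stated in advance; only the rule from result to N is absent. Nothing says outright that 0.255 was observed, and the fit to round inputs suggests that some values were assumed. At SD 1 and correlation 0.2, moving from 50 to 60 lowers the conditional error. All of this stands.

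A reader might infer that the interim was in effect a hypothesis test, or that the pain result will carry a materially inflated error rate. The documents support neither: the source of 0.255 is an inference, and the only sample sizes they give around the re-estimation are 50 through 60, where even the worst case is about 5.5%. Requiring a stage-wise primary test on that basis would be out of proportion.

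**Conclusion.** The point holds as an inconsistency in the enrolment target and an avoidable weakness in the powered pain comparison. The gap between targets is worth about 8 percentage points of power (75% against 83%), conditional on f = 0.40319 and 10% attrition.

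That the powered effect includes the pre-acupuncture reading is a strong inference from the four measurements and the visit schedule, not an explicit statement. The illustrative loss (59% against 80%) rests on the assumed difference, SD and correlation, and is not an estimate of this trial's actual power.

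The 81% is correct arithmetic, but only for inputs whose origin is not stated. The re-estimation is a disclosure gap. It does not show that the 5% level is lost. Confidence is medium, because the model terms and the source of the inputs are not given.

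**What to change.** 1. In section 3.1 give 60 (30 per group). In section 11 mark 50 as the original pre-interim figure, explain how 60 fits with 50 as the feasible maximum, and state that no further re-estimation will be made.
2. Before the final data are analysed, name the pain comparison: the between-group effect over PACU arrival, 1 h and 3 h in the mixed model, with pre-operative (pre-acupuncture) pain as a baseline covariate and not as an outcome reading. Table 1 lists that reading as NPS in one arm and VAS in the other, so confirm that both arms used the same scale.
3. State which of the difference, SD and correlation came from interim data by arm and which were assumed, and describe the 81% as conditional on them. If the interim arm difference was used, disclose it. A fixed-weight combination, Z = √(31/50) × Z1 + √(19/50) × Z2 (weights 0.787 and 0.616), can be reported at most as a sensitivity analysis, with the first 31 patients as stage one. If the difference was not used, say so.

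The cost is protocol and SAP wording and one named model. The pre-operative pain score is already scheduled in both arms, so no new data are needed.
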